4.1. Statistical Hypotheses

No statistical hypotheses are planned for this study.

4.2. Sample Size

The sample size is empiric and selected to support assessment of safety, tolerability, and PK parameters. Approximately 15 participants will be enrolled to allow for at least 9 participants (3 per cohort) to "complete" (ie. participant completed EoT assessments, all PK/PD sampling was performed within window, and all doses were received per the SoA) the study.

4.3. Randomization, Stratification, and Blinding

This is a Phase 1, open-label study; therefore, there will be no randomization, stratification, and blinding of study participants in this study.

Statistical Analysis Plan, Version **1.0**Date Issued: 26/04/2022

4.4. Analysis Sets

The following analysis sets will be used in the statistical analyses:

- Safety Set: The Safety Set will include all participants who receive any amount of study drug. Participants will be analyzed according to the study drug received.
- Pharmacokinetic Set: The PK Set will include all treated participants for whom the PK profile of ALXN1850 can be adequately characterized. Pharmacokinetic analyses will be based upon the study drug received.
- Pharmacodynamic Set: The PD Set will include all treated participants for whom the PD profile of ALXN1850 can be adequately characterized.
- Immunogenicity Analysis Set: The Immunogenicity Analysis Set will include all treated participants who received any study drug and who after the first dose have at least one reportable result in the ADA assay. Anti-drug antibody analysis will be conducted based on the actual treatment they receive.

5. Participant Disposition

5.1. Disposition

Using the enrolled set, the screen failure of participants will be summarized with counts and percentages by overall. A summary table will include the following:

- Number of participants in the enrolled set (ie, all participants who signed the informed consent form [ICF])
- Number of participants who were screen failures
- Number of participants who received a dose
- Number of participants who failed screening due to COVID-19 related reasons
- Reason for screen failure that was not due to eligibility
- Reason for screen failure that was due to eligibility

Based on the Safety Set, the analysis sets will be summarized with counts and percentages by cohort and overall. A summary table will include the following:

- Number of participants included in PK Set
- Number of participants excluded from the PK Set
- Reason for exclusion from the PK Set
- Number of participants included in PD Set
- Number of participants excluded from the PD Set
- Reason for exclusion from the PD Set
- Number of participants included in Immunogenicity Set
- Number of participants excluded from the Immunogenicity Set
- Reason for exclusion from the Immunogenicity Set

Using the Safety Set and PK Set, the disposition of participants will be summarized with counts and percentages by cohort and overall. A summary table will include the following:

Statistical Analysis Plan, Version 1.0 Date Issued: 26/04/2022

- Number of participants who completed the study
- Number of participants who discontinued the study
- Reasons for discontinuation
- Number of participants who discontinued the treatment
- Reasons for treatment discontinuation
- Number of participants who were discontinued due to COVID-19

Screen failure data will be presented in a data listing for all screen failure participants. Participant disposition data and analysis sets will be presented in separate data listings for the Safety Set.

5.2. **Protocol Deviations**

The protocol deviations will be summarized by cohort and overall for the Safety Set. Protocol deviations will be classified as important and not important.

All protocol deviations will be presented in a data listing for the Safety Set.

5.3. **Inclusion and Exclusion Criteria**

Inclusion and exclusion criteria deviations will be presented in a data listing for the Safety Set.

6. Demographics and Baseline Characteristics

Demographics 6.1.

Age, sex, race, ethnicity, height, and body mass index (BMI) will be collected at Screening only; weight will be collected at Screening, on Day -1, and on Day 14, Day 21, and Day 28 for first participant within each cohort, and on Day 7, Day 14, and Day 21 for subsequent participants within each cohort.

Descriptive statistics will be calculated for the following continuous demographic characteristics:

- Age (years)
- Weight (kg)
- Height (cm)
- BMI (kg/m^2)

Frequency counts and percentages will be tabulated for the following categorical variables:

- Sex
- Race
- Ethnicity

The summaries will be presented by cohort and overall for the Safety Set. The last weight measurement collected before the first dose will be used as baseline for the summary.

Demographic characteristics will be presented in a data listing for the Safety Set.

6.2. Alcohol Test and Urine Drug Screen

An alcohol test will be performed at Screening. A urine drug screen (includes amphetamines; barbiturates; benzodiazepines; cocaine; opiates; phencyclidine; methamphetamine; 3,4 methylenedioxy-methamphetamine; and methadone) will be performed at Screening, on Day -1, and on Day 14, Day 21, and Day 28 for first participant within each cohort, and at screening, Day -1, Day 7, Day 14, and Day 21 for subsequent participants within each cohort.

Statistical Analysis Plan, Version 1.0

Date Issued: 26/04/2022

Urine alcohol and drug screen results will be presented in a separate data listing.

6.3. Medical History

Medical history data will be collected at Screening.

Medical history data will be coded using the Medical Dictionary for Regulatory Activities (MedDRA, version to be delineated in the clinical study report [CSR]) and presented in a data listing for the Safety Set.

6.4. Genetic

To confirm eligibility, genetic testing for *ALPL* gene variant may be performed during the Screening.

Genetic testing results will be listed for the Safety Set.

7. Treatments and Medications

7.1. Prior and Concomitant Medications

Medications that stop prior to the first dose of study drug will be classified as prior medication. Medications that start on or after the first dose of study drug will be classified as concomitant. If a medication starts before the first dose of study drug and stops on or after the first dose of study drug, then the medication will be classified as both prior and concomitant.

All prior and concomitant medications will be coded according to the World Health Organization Drug Dictionary (version to be delineated in the CSR).

Prior concomitant medications will be summarized by cohort and overall for the Safety Set. Concomitant medications will be summarized by cohort and overall for the Safety Set.

All prior and concomitant medications will be presented in a data listing for the Safety Set.

7.2. Medical or Surgical Treatment Procedures

Medical or surgical treatment procedures will be coded using the MedDRA (version to be delineated in CSR) and will be presented in a data listing for the Safety Set.

7.3. Study Treatment

The study drug composition and doses to be administered in this study are presented in the protocol. Decisions to continue, modify (explore the dose cohort further), o r escalate dosing will be made by the SRC.

The study drug administration and drug accountability data as collected on electronic case report form (eCRF) will be presented in the data listings for the Safety Set.

8. Pharmacokinetics

The Safety Set will be used for PK concentration listings and individual figures, and the PK Set will be used for PK parameter listings, all summary tables, mean figures and statistical analyses.

8.1. Data Handling

Plasma concentrations that are below the limit of quantification (BLQ) will be treated as zero for calculation of descriptive statistics. Individual values that are BLQ will be presented as "BLQ" in the concentration data listing. For the presentation of summary and order statistics, if at least 1 participant has a concentration value BLQ for the time point, then the minimum value will be displayed as "BLQ". If more than 25% of participants have a concentration data value of BLQ for a given time point, then the minimum and the first quartile [Q1] will be displayed as "BLQ". If more than 50% of the participants have a concentration data value of BLQ for a given time point, then the minimum and median values will be displayed as "BLQ". If more than 75% of the participants have a concentration value of BLQ for a given time point, the minimum, Q1, median, and third quartile [Q3] values will be displayed as "BLQ". If all participants have concentration data values BLQ for a given time point, then all order statistics (minimum, Q1, median, Q3, and maximum) will be displayed as "BLQ", and the SD and coefficient of variation (CV) will be reported as not applicable, otherwise the calculated mean will be presented.

For PK parameter calculations, BLQ values will be treated as zero with the exception that a BLQ value between 2 quantifiable concentrations will be set as missing. If consecutive BLQ concentrations are followed by quantifiable concentrations in the terminal phase, those concentrations after BLQ concentrations will be treated as missing.

Data rounding specifications for PK data are documented in the PK TLF shells.

8.2. Plasma Pharmacokinetic Concentrations

Blood samples for analysis of concentrations of ALXN1850 in plasma for each of the treatments will be collected at the following time points:

First participant within each cohort	Subsequent participants within each cohort
Day 1: pre-dose, EOI, and 2h, 6h,, and 12h	Day 1: pre-dose, EOI, and 2h, 6h,, and 12h
post dose (IV dose)	post dose (IV dose)
Day 2 (24 hours post IV dose)	Day 2 (24 hours post IV dose)
Day 3 (48 hours post IV dose)	Day 3 (48 hours post IV dose)
Day 5 (96 hours post IV dose)	Day 5 (96 hours post IV dose)
Day 8 (168 hours post IV dose)	
Day 15: pre-dose and 2h, 6h, and 12h post	Day 8: pre-dose and 2h, 6h, 8h, and 12h post
dose (SC dose 1)	dose (SC dose 1)
Day 16 (24 hours post SC dose 1)	Day 9 (24 hours post SC dose 1)
Day 17 (48 hours post SC dose 1)	Day 10 (48 hours post SC dose 1)
Day 19 (96 hours post SC dose 1)	Day 12 (96 hours post SC dose 1)
-	
Day 22: pre-dose and 2h, 6h, and 12h post	Day 15: pre-dose and 2h, 6h, and 12h post
dose (SC dose 2)	dose (SC dose 2)
Day 23 (24 hours post SC dose 2)	Day 16 (24 hours post SC dose 2)

Page 12 of 29

Day 29: pre-dose and 2h, 6h, and 12h post	Day 22: pre-dose and 2h, 6h, and 12h post
dose (SC dose 3)	dose (SC dose 3)
Day 30 (24 hours post SC dose 3)	Day 23 (24 hours post SC dose 3)
Day 31 (48 hours post SC dose 3)	Day 24 (48 hours post SC dose 3)
Day 36 (168 hours post SC dose 3)	Day 29 (168 hours post SC dose 3)
Day 51 (3 weeks post SC dose 3)	Day 43 (3 weeks post SC dose 3)
Day 65 (5 weeks post SC dose 3)	Day 57 (5 weeks post SC dose 3)
Day 85 (8 weeks post SC dose 3)	Day 78 (8 weeks post SC dose 3)

Individual plasma concentrations of ALXN1850 for each treatment will be presented in data listings and summarized separately using descriptive statistics (N, n [non-missing values within the population], arithmetic mean, SD, %CV, median, minimum, and maximum) by cohort, study day, and scheduled time point. All participants (first and subsequent) will be summarized together for Days 1-8 (predose) for each cohort, after Day 8 only subsequent participants data will be summarized and whereas first participant data will be presented separately. An additional sensitivity analysis will be performed by combining subsequent participants with the first participant (following each SC dosing, ie, SC Dose 1, SC Dose 2, and SC Dose 3) whe re data (corrected from prior carryover exposure post IV dose) is summarized by cohort and scheduled timepoints relative to each dose.

Individual plasma concentrations for ALXN1850 will be plotted for each participant by actual time on both linear and semi-logarithmic scales. Mean plasma concentrations of ALXN1850 versus nominal time will be plotted for each treatment on both linear and semi-logarithmic scales. In addition, mean plasma concentrations of ALXN1850 versus nominal time will be plotted for each treatment by ADA status on both linear and semi-logarithmic scales. The definition of ADA status (ADA negative and ADA positive, and/or pre-existing immunogenicity, treatment-emergent ADA responses, and treatment-boosted ADA responses if data permits, the definition for the ADA response categories is described in the Section 11 of Immunogenicity Analysis).

Individual and mean plasma trough concentrations (C_{trough}) for ALXN1850 versus day following subcutaneous dose administration will be plotted on both linear and semi-logarithmic scales. Time to reach steady state will be graphically assessed by plotting mean plasma C_{trough} concentration versus study day in both linear and semilogarithmic scales.

In addition, attainment of steady state will be assessed via stepwise, linear mixed regression models with a random subject effect among subsequent participants. The analysis will be stratified by cohort. This approach involves an examination of Ctrough concentrations over time using mixed regression models and calculating a slope and corresponding 95% CI. Predose assessments on day 8, day 15, and day 22 will be used. The model results will be evaluated to see if 0 is included in the 95% CI which indicates that the steady state was achieved.

Plasma PK concentrations of ALXN1850 will be reported to 3 significant figures in summary statistics except for %CV which will be reported to 1 decimal place and N and n which will be reported as integers.

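### SAP 8.2 reads a trough-slope confidence interval that includes 0 as proof of steady state, with no margin, about 4 participants per cohort, and a post-IV Day 8 value in the slope

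*SAP*

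**What the plan says.** SAP 8.2 assesses steady state in two ways. The first is a plot: "Time to reach steady state will be graphically assessed by plotting mean plasma" troughs against study day, with no criterion for reading it. The second is a regression. Attainment is "assessed via stepwise, linear mixed regression models with a random subject effect among subsequent participants", and "The analysis will be stratified by cohort". The data are fixed: "Predose assessments on day 8, day 15, and day 22 will be used". The decision rule is: "The model results will be evaluated to see if 0 is included in the 95% CI which indicates that the steady state was achieved". The SAP states no margin, minimum precision or minimum number of participants, and it does not describe the steps behind *stepwise*.

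The SAP 8.2 sampling table lists "Day 8: pre-dose and 2h, 6h, 8h, and 12h post" dose for SC dose 1 in subsequent participants, so the Day 8 trough precedes all SC drug. Protocol 6.6.1 describes Day 8 in these participants as 168 hours after the IV dose. The table also lists "Day 29 (168 hours post SC dose 3"), which the regression does not use. SAP 4.2 says: "Approximately 15 participants will be enrolled to allow for at least 9 participants (3 per cohort") to complete. The protocol synopsis plans about 5 per cohort.

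SAP 8.3 derives CL/F and Vd/F only if the trough can attain steady state. It does not name the regression as the gate, but the SAP contains no other criterion.

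**The concern.** A confidence interval that includes 0 says that the data do not exclude a flat slope. It does not say that they exclude a rising one. Without a margin the rule rewards imprecision: the smaller or noisier the cohort, the wider the interval and the more readily steady state is declared.

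The choice of days is a separate problem. Day 8 reflects one IV dose. Days 15 and 22 follow SC doses 1 and 2 and still carry some IV drug. The slope across the three is therefore not SC accumulation. Depending on half-life and absorption, Day 8 can lie well below the SC plateau or slightly above it.

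At stake is a sentence in the study report that steady state was or was not achieved, and whether CL/F and Vd/F are reported as steady-state parameters, driven mainly by cohort size, assay noise or the route switch.

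**Working it through.** The plan gives no power or precision figure for this assessment, so there is none to reproduce.

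**Participants per model.** The first participant is left out: 5 − 1 = 4 as planned. If only 3 remained and one were the first participant, 3 − 1 = 2.

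**Precision from the design alone.** With three weekly troughs and a random intercept, SE(slope per week) = s/√(2n) with 2n − 1 degrees of freedom, where s is the within-participant SD. The documents give no CV; I assume 15% or 25%. The 95% half-width at n = 4, as a share of the mean trough per week, is:
- CV 15%: 2.365 × 0.15/√8 = 12.5%
- CV 25%: 2.365 × 0.25/√8 = 20.9%

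At CV 25% it grows to 26% for n = 3 and 40% for n = 2. Any estimated rise smaller than the half-width is called steady state.

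**Half-life, for illustration.** No value is stated, and two readings are possible.
- The Amendment 4 rationale (Protocol 10.9) equates the end-of-treatment visit with 5.5 half-lives. Counting from Day 22 to Day 57: 35/5.5 = 6.36 d.
- Table 5 (Protocol 4.3), Cohort 1: IV AUC/Cmax = 325/4.3 = 75.6 h. Solving (1 − e^(−168k))/k = 75.6 gives about 2.6 d. The SC/IV ratio 441/325 = 1.36, set equal to 0.75/(1 − e^(−7k)) with k per day, gives 6.0 d if the SC AUC is at plateau.

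One compartment does not fit both Table 5 readings, so I use 6.36 d and 2.6 d as two scenarios.

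**Expected troughs.** Superposition with IV on Day 1, SC on Days 8, 15 and 22, F = 75% (Protocol 4.3) and assumed absorption half-life 0, 1 or 2 d:
- 6.36 d: Day 22 is 94/91/88% of the SC plateau and Day 29 is 97/96/94%. Troughs are still rising.
- 2.6 d: Day 22 is 100/99/97% of plateau, but Day 8 is 113/73/55%.

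**How often the rule says *achieved*.** I simulated 40,000 cohorts per scenario: lognormal, between-participant CV 40%, one untransformed fit. Ranges run over absorption half-life.

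| Half-life; days in fit | n | CV 15% | CV 25% |
|---|---|---|---|
| 6.36 d; 8/15/22 | 4 | 9–48% | 46–77% |
| 6.36 d; 8/15/22 | 12 (hypothetical) | 0–3% | 2–34% |
| 6.36 d; 8/15/22 | 2 (extreme) | 55–80% | 79–90% |
| 6.36 d; 15/22/29 | 4 | 58–86% | 82–92% |
| 2.6 d; 8/15/22, absorption 1–2 d | 4 | 6–44% | 37–74% |
| 2.6 d; 8/15/22, absorption near-instant | 4 | 86% | 92% |

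Rows 1 to 3 show that less data favours *achieved*. Row 4 shows that replacing Day 8 by Day 29 under the same rule makes the call more frequent. Row 5 shows the opposite error: Day 22 is at 97–99% of plateau, yet the low Day 8 value yields *not achieved* in 56–94% (CV 15%) or 26–63% (CV 25%).

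**Limits of a change of days.** At 6.36 d the IV dose leaves 2^(−14/6.36) = 0.217 on Day 15, against totals of 0.57–0.63 (relative to dose/volume). So 34–38% of the Day 15 value is still IV drug. The Day 29 visit has a ±1 day window (Protocol Table 2). One day's shift moves the true Day 29/Day 22 ratio from 1.04–1.08 to 0.93–1.16 at 6.36 d, and from about 1.0 to 0.76–1.30 at 2.6 d.

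**The case against.** **Little depends on the result.** Steady state is not an objective or endpoint, no hypotheses are planned, and the sample size is empiric. The accumulation ratio and F do not use the call. At 6.36 d, Dose/AUCtau after dose 3 overstates CL/F by only 3–8%. This stands and limits the size of the point. It does not rescue the rule, because the SAP prescribes a yes/no conclusion where it could have reported an estimate.

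**Calling *achieved* wrong presupposes a threshold.** At 88–94% of plateau on Day 22, some would accept steady state. This stands: the percentages are not error rates. They show how the call moves with n and noise when the truth is held fixed.

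**Two participants is not the planning case.** The minimum of 3 counts completers, whereas the model runs on the PK Set without a completer filter. A participant lost after Day 22 can still supply all three troughs. This stands; about 4 is the number to plan on.

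**The fitted procedure is unknown.** If *stepwise* means dropping the earliest day, the false *not achieved* at 2.6 d largely disappears. On the same reading, Days 15 and 22 alone give *achieved* in 85–95% of cohorts at 6.36 d and n = 4. The ambiguity is itself a reason to define the steps.

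A reader might also infer that Day 8 always pushes towards *achieved*. It does not: at 6.36 d it is the lowest point and makes that call harder.

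**Conclusion.** The rule is wrong as written. Non-significance is read as proof, per cohort, with about 4 participants and no margin. The Day 8 point is a post-IV value that prevents the slope from being read as SC accumulation. Neither conclusion rests on an assumption.

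The size is modest. What is exposed is a reported statement about steady state and the status of CL/F and Vd/F, not an endpoint. The SAP should be corrected, but the trial's conclusions on safety, F or accumulation are not threatened.

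The percentages rest on assumed half-life, absorption, CVs, one compartment and a single fit. A reader might infer that the study will falsely declare steady state in some stated share of cohorts. The documents do not support that, because they give neither the variability nor a definition of steady state against which to count errors.

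**What to change.** 1. Delete the sentence that an interval including 0 indicates steady state. Report, per cohort, the change between successive troughs (log-scale slope or geometric mean ratio) with its CI. State steady state only if that CI lies within a margin the sponsor prespecifies. Otherwise report *not demonstrated*, and label SC Dose/AUCtau after dose 3 as such, not as steady-state CL/F; likewise do not report Vd/F as a steady-state value.
2. Define the steps, or delete *stepwise*.
3. Do not treat Day 8 as an SC trough. Use Days 15 and 22. Add Day 29 only with a written sampling-time rule, for example only samples close to 168 h, or values adjusted to 168 h with the participant's own terminal slope. Recording actual times does not by itself correct a simple ratio. Say that Day 29 counts although it is not predose under the SAP 8.3 trough definition.
4. State that measured Day 15 and Day 22 values still contain IV drug. A carryover-corrected version can be added, but its method must be written: SAP 8.2 mentions correction only for a descriptive sensitivity summary and gives none, and SAP 8.3 lists corrected values only for Cmax and AUCtau.

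Items 1 and 3 must change together, because dropping Day 8 under the present rule makes *achieved* more frequent.

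The cost is SAP wording; the Day 29 sample is already scheduled. The downside is that *not demonstrated* will be common. The 90% CI for a ratio of two successive troughs is the estimate multiplied or divided by exp(t(0.95, n − 1) × s × √(2/n)), with s on the log scale. At n = 4 that factor is 1.28 (CV 15%) to 1.51 (CV 25%), before any error from sampling time or carryover correction.

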8.3. Plasma Pharmacokinetic Parameters

The plasma concentration-time data for ALXN1850 will be analyzed by non-compartmental analysis using Phoenix® WinNonlin® Version 8.0 or higher (Certara USA, Inc., Princeton, New Jersey). The following PK parameters will be derived for ALXN1850 based on actual date and times calculated relative to the actual date and time from the start of dose administration (for example, start of infusion) in each dosing period, where data permit. If missing actual sampling dates and times, then the nominal time relative to the start time of the administration will be used.

C _{max}	Maximum observed plasma concentration
C _{max_corrected}	Maximum observed plasma concentration (for SC dose only if carryover from IV exposure is observed)
C _{trough}	Trough (predose) concentration observed at the start of the dosing interval (C _{trough})
T _{max}	Time of maximum observed concentration
AUCt	Area under the curve (AUC) from time 0 to the last quantifiable concentration, calculated using the linear trapezoidal rule
AUC _{168h}	Area under the curve (AUC) from time 0 to 168h, calculated using the linear trapezoidal rule (for IV dose only)
AUC _{inf}	AUC from time 0 extrapolated to infinity, calculated using the linear trapezoidal method (IV dose only)
AUC _{tau}	AUC within the dosing interval, calculated using the linear trapezoidal method (SC dose only)
AUC _{tau_corrected}	AUC within the dosing interval, calculated using the linear trapezoidal method (for SC dose only if carryover from IV exposure is observed)
t _{1/2}	Apparent terminal elimination half-life, calculated as: ln (2) / Kel
CL	Total body clearance calculated as: Dose / AUC _{inf} (For IV dose only)
CL/F	Apparent total body clearance calculated as: Dose / AUC _{tau} at steady state (For SC dose and only if C _{trough} can attain steady state)
V_d	Volume of distribution during the terminal phase, calculated as: Dose / $[\lambda_z * AUC_{inf}]$ (For IV dose only)
V _d /F	Apparent volume of distribution during the terminal phase, calculated as: Dose / [λ_z * AUC _{tau} at steady state] (For SC dose and only if C _{trough} can attain steady state)
R	Subcutaneous accumulation ratio (AUC _{tau_SC} 3rd dose / AUC _{tau_SC} 1st dose)
F	Absolute bioavailability after subcutaneous administration, $F = AUC_{tau}$ (SC) / AUC_{inf} (IV)

In addition to the above PK parameters, which will be listed and summarized, the following parameters will also be listed to document the selection of data points used to estimate $T_{1/2}$ using non-compartmental procedures:

λ_z	Terminal phase elimination rate constant
Number points	Number of data points used to estimate λ_z ; a minimum of 3 data points must be used, and C_{max} must not be included
λ_z lower	Lower bound used for the estimation of λ_z
λ_z upper	Upper bound used for the estimation of λ_z
Rsq	r^2 , the coefficient of determination (goodness of fit statistic); λ_z and all associated parameters will only be reported where $r^2 \ge 0.80$
%AUC _{extrap}	Percentage of AUC_{inf} due to extrapolation; If % $AUC_{extrap} > 20\%$ then, AUC_{inf} , CL, and V_d , will not be summarized

Additional plasma PK parameters may be calculated if deemed appropriate.

Plasma PK parameters for ALXN1850 will be presented in data listings and summarized separately using descriptive statistics (n, arithmetic mean, SD, %CV, geometric mean, geometric %CV, median, minimum, and maximum) by treatment. T_{max} will be summarized using the descriptive statistics median, minimum, and maximum only. Plasma PK will be presented by ADA status in figures. In addition, the Plasma PK parameters and ADA titers will be presented in the overlay figures for each subject overtime.

Plasma PK parameters of ALXN1850 will be reported to 3 significant figures in summary statistics except for %CV which will be reported to 1 decimal place and N and n which will be reported as integers.

